For measles, the most recent national serological survey was conducted in 2013. To evaluate the sample size needed to estimate the current seroprevalence by age, we use a cohort-based modelling approach to project immunity levels to 2025. This model incorporates historical vaccination coverage, age of vaccination and waning immunity, following methods described by Hens et al. (2015) and Abrams et al. (2014) (30,31). The aim was to obtain both overall and agegroup-specific seroprevalence estimates with a precision of +-2% (width of confidence interval max. 4%). To ensure sufficient sample size of the serumbank for pathogens other than measles, these calculations were repeated for 2 additional pathogens. The additional pathogens (CMV and Hepatitis B) were selected based on their seroprevalence patterns in the population who differ importantly from the measles seroprevalence patterns.

Appendix 5 contains the full methodology and results. With a total sample size of 3,900 samples, precision of overall national seroprevalence estimates for all 3 pathogens would be <2% (and even <1% for measles and Hepatitis B). Not all agegroup-specific estimates would have <2% precision, but all are within acceptable ranges (all <3% precision for measles). To obtain equal precision in the region-specific estimates, similar absolute number of samples would need to be collected from Flanders, Walllonia and Brussels. However, as both the population size as well as

the number of labs in Brussels is much smaller than in Flanders, this is deemed unfeasible. We therefore plan a pragmatic approach and adjust the regional allocation to reflect practical constraints and the actual number of participating laboratories, accepting wider confidence intervals in Brussels. The final distribution of samples by agegroup is then presented in Table 1.

Table 1. Samples distribution - National

Age groups	Number of samples - National
1-4yo	450
5-9yo	450
10–14yo	300
15-19yo	450
19-31yo	450
31-40yo	750
40-65yo	1050
Total	3900

Sample collection and analysis

Sample collection and transport

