Hep E	• Anti-HEV	• All ages	 Assess real burden and transmission dynamics of HEV which is the most common cause of acute viral hepatitis world-wide and can lead to severe outcomes. There is no solid surveillance in place for HEV (very few samples sent to NRC), but it seems that there is a rising trend both in Belgium and in Europe. It is currently unclear to what extend this is due to increased detection or a true increase. Compare results with previous study Better understanding of the epidemiology of HEV in Belgium may allow for planning of more actions in the food industry. 	2006-2014, Belgium
Influenza A	 anti-H5 (HI) anti-H7 (HI) anti-H9 (HI) 	All ages	 Assess the prevalence of asymptomatic cases (undetected infections) resulting from prior zoonotic exposure to animal influenza viruses in Belgium to provide complementary evidence for risk assessments and public health preparedness measures. Evaluate the zoonotic potential of specific virus subtypes across different age groups. 	

			 Assess the severity and fatality rates, acknowledging potential overestimation due to undetected cases. Determine immunity levels in the general population based on seroprevalence data. 	
Measles	 Anti- measles IgG 	• All ages	 Increasing incidence of measles, important public health problem WHO elimination goals Unclear population immunity in children as last survey in infants from 2019, important methodological changes in planned vaccine coverage studies Unclear population immunity in adolescents in Brussels, as not all are captured by current vaccine coverage studies Unclear population immunity in adults due to lack of historical records and potential of waning immunity 	Belgium 2002, 2006, 2013
Mumps	 Anti- mumps IgG 	All ages	 Waning immunity and outbreaks in adolescents, unclear optimal timing of MMR vaccine in schedule Compare with previous studies Integrate with findings on measles and rubella as part of 1 combination vaccine 	
Rubella	Anti- rubella IgG	All ageswomen of reproducti ve age	 Congenital rubella = WHO target for elimination Unclear optimal timing of MMR vaccine in vaccination schedule 	
Pertussis	● anti-PT IgG	All ages	 Recent important increases in incidence; unclear which proportion reflects an increased reporting versus a true rise in cases Waning immunity over time, unclear optimal timing of booster vaccinations Compare findings with previous studies to understand evolution over time 	

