1.4. Simulation framework for sample allocation and precision

To assess the precision obtained under different age-based sampling structures, we simulated synthetic datasets by drawing binomial outcomes from the projected age-specific seroprevalence profile (Section 1.2). For each individual in the simulated sample, seropositivity status was assigned using a Bernoulli distribution with probability equal to the predicted seroprevalence at their age. This process was repeated independently 500 times for each sampling scenario. The resulting datasets were used to estimate the seroprevalence in each of the eight predefined age groups. Following the approach described by Blaizot et al. (2019) [1], precision was defined as half of the width of the 95% simulation-based confidence interval across the 500 replicates (simulation runs), calculated for each age group and overall. This framework enabled direct comparison of the expected estimation precision under each sampling design.

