2.3. Allocation of samples for CMV

We estimated age-specific cytomegalovirus (CMV) seroprevalence using data from the 2011 Belgian serological survey. Figure S5 displays the observed seroprevalence and the fitted estimates obtained from a GAM. These model-based estimates were used to simulate the precision of overall CMV seroprevalence under various sample sizes and sampling strategies.

Figure 9 summarizes the results from 500 simulations, showing the mean, median, and 95% confidence intervals of overall seroprevalence across four total sample sizes (1,000 to 9,000) and three sampling structures (survey-based, population-based, and uniform). The three sampling designs yielded very similar results. The population-based structure showed slightly better precision at 1,000 samples, whereas the survey-based design performed best at 3,000 samples.

Based on these results, we recommend allocating at least 1,000 samples per region for CMV, corresponding to 3,000 samples nationally. With this total sample size, the estimated precision for the overall CMV seroprevalence at the national level ranges between $\pm 2.8\%$ and $\pm 3.4\%$, depending on the sampling strategy. Although this is sufficient for generating national estimates, it does not provide acceptable precision for regional-level estimates. To ensure adequate precision at the regional scale (e.g., $\pm 2\%$), a higher number of samples per region would be required. Detailed precision values for each sample size and sampling design are provided in Supplementary Table S3.

[figure not shown]

Figure 9. CMV serological data: mean, median and 95% confidence interval for the overall seroprevalence over 500 simulations as a function of the total number of sampled individuals.

3. Conclusions

We recommend allocating 3,900 samples nationally, corresponding to approximately 1,300 samples per region (Flanders, Brussels, and Wallonia), to ensure acceptable precision (below $\pm 2\%$) for estimating the overall seroprevalence of measles, hepatitis B, and CMV at the regional level.

An optimisation algorithm was used to test multiple age-based sampling distributions and identify the most efficient allocation for each pathogen. Table 2 summarises the optimal proportions of samples by age group, which differ slightly across pathogens. These proportions were then translated into absolute sample counts (Table 3), assuming 3,000 samples per pathogen at the national level.

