To ensure sufficient precision for all pathogens, we selected the maximum number of samples per age group across the three pathogens as the final recommendation. This results in a total of 3,900 samples nationally, which we divide equally across the three regions, yielding 1,300 samples per region.

Table 4 reports the expected precision of the overall seroprevalence estimates under this allocation. At the national level (3,900 samples per pathogen), the expected precision is 0.82% for measles, 0.85% for hepatitis B, and 1.69% for CMV. At the regional level (1,300 samples per region), expected precision decreases slightly to 1.69% for measles, 1.45% for hepatitis B, and 2.64% for CMV, still within acceptable bounds.

Age group	Measles	НерВ	CMV
1-4yo	5%	5%	15%
5-9yo	15%	15%	5%
10-14yo	5%	10%	10%
15-19yo	15%	5%	10%
19-31yo	15%	10%	10%
31-40yo	20%	25%	15%
40-65yo	25%	30%	35%
Precision	0,88%	0,74%	1,52%

Table 2. Optimal proportion of samples per age group for measles, hepatitis B, and CMV based on national-level simulations.

	Measles	НерВ	CMV	National	Regional
1-4yo	150	150	450	450	150
5-9yo	450	450	150	450	150
10-14yo	150	300	300	300	100
15-19yo	450	150	300	450	150
19-31yo	450	300	300	450	150
31-40yo	600	750	450	750	250
40-65yo	750	900	1050	1050	350
Total	3000	3000	3000	3900	1300

Table 3. Absolute number of samples per age group, assuming 3,000 samples per pathogen. The final allocation (bold values) corresponds to the highest required count across pathogens, resulting in a total of 3,900 samples nationally (or approximately 1,300 per region).

	Measles	НерВ	CMV
National	0,82%	0,85%	1,69%
Regional	1,69%	1,45%	2,64%

Table 4. Expected precision (half-width of the 95% simulation-based confidence interval) for overall seroprevalence estimates under the final allocation. National precision is based on 3,900 samples; regional precision is based on 1,300 samples per region.

Precision by age - national allocation

_	.=			
Age group	Allocation	Measles	НерВ	CMV
1-4yo	450	2,25%	0,50%	4,23%
5-9yo	450	2,61%	0,53%	3,25%
10-14yo	300	1,76%	0,63%	3,50%
15-19yo	450	1,95%	0,73%	3,14%
19-31yo	450	2,88%	1,20%	2,94%
31-40yo	750	2,40%	1,51%	2,78%
40-65vo	1050	1,25%	1.42%	3.02%

Table 5. Expected precision (half-width of the 95% simulation-based confidence interval) for prevalence estimates of each age group under the final allocation.

4. References of Appendix 5

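### Appendix 5 states regional precision for 1,300 samples in every region, a split the Sample size section rejects because of Brussels; its below-±2% regional conclusion also fails for CMV even at 1,300

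*Protocol*

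**What the plan says.** Appendix 5, section 3 (Conclusions), recommends 3,900 samples nationally, "corresponding to approximately 1,300 samples per region (Flanders, Brussels, and Wallonia), to ensure acceptable precision" below ±2% for overall seroprevalence of measles, hepatitis B and CMV at regional level. It then states: "This results in a total of 3,900 samples nationally, which we divide equally across the three regions, yielding 1,300 samples per region". Table 4, captioned as the final allocation, reports half-widths of 0.82%, 0.85% and 1.69% nationally and 1.69%, 1.45% and 2.64% regionally (measles, hepatitis B, CMV). Its caption adds: "National precision is based on 3,900 samples; regional precision is based on 1,300 samples per region".

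The Sample size section of the main text says that equal regional precision would need similar absolute numbers from Flanders, Wallonia and Brussels. It judges this unfeasible because Brussels has a much smaller population and far fewer laboratories than Flanders. The plan is instead to "adjust the regional allocation to reflect practical constraints and the actual number of participating laboratories, accepting wider confidence intervals in Brussels". Table 1 of the main text gives national counts by age group only. The Sampling procedure section allocates samples to laboratories in proportion to population density in their area, which does not fix a Brussels count either.

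**The concern.** The protocol contains one set of regional precision figures, and it is computed for a regional split that the main text sets aside. The main text also refers the reader to Appendix 5 for the full methods and results, so anyone looking for the expected regional precision arrives at Table 4.

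This bears on a stated aim. The Objectives include measles seroprevalence by geographical area and region as a risk factor for susceptibility. Brussels is also where the protocol says other information is thin: Appendix 1 gives as one reason for including measles "Unclear population immunity in adolescents in Brussels, as not all are captured by current vaccine coverage studies". A reader of Appendix 5 would expect Brussels to be estimated as precisely as the other regions, within ±1.69% for measles and ±1.45% for hepatitis B. The same reader would take the ±2% conclusion to cover CMV.

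**Working it through.** **Inputs.** Precision is "half of the width of the 95% simulation-based confidence interval across the 500 replicates" (Appendix 5, section 1.4). Regional values come from Table 4, the overall prevalences (measles about 0.903, hepatitis B about 0.055, CMV about 0.348) and precision by sample size from Tables S1–S3, and the total of 3,900 from Table 1 of the main text. The simulation cannot be rerun because the projected age profiles are in figures that are not available.

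**1. Do the stated regional values fit n = 1,300?** The regional column of Table 3 sums to 150+150+100+150+150+250+350 = 1,300. Three approximations to the half-width:

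| | Stated | Binomial, 1.96·√(p(1−p)/1300) | Tables S1–S3 at n=1,000, times √(1000/1300) | National Table 4 value times √3 |
|---|---|---|---|---|
| Measles | 1.69% | 1.61% | 1.41–1.71% | 1.42% |
| Hepatitis B | 1.45% | 1.24% | 1.13–1.27% | 1.47% |
| CMV | 2.64% | 2.59% | 2.53–3.05% | 2.93% |

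The stated values are of the right size for 1,300, though no single approximation reproduces all of them. They are therefore values for 1,300 samples and not for a smaller Brussels count.

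**2. Brussels count at which ±2% is reached.**

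- Scaling Table 4, n = 1300·(h/2)²: measles 1300·(1.69/2)² = 928; hepatitis B 1300·(1.45/2)² = 683.
- Scaling Tables S1–S2 from n = 1,000, n = 1000·(h/2)²: measles 648 (h = 1.61%) to 951 (h = 1.95%); hepatitis B 417 (h = 1.291%) to 528 (h = 1.453%).

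**3. Half-width at assumed Brussels shares.** The documents give no share, so 10%, 15% and 20% of 3,900 are assumptions. The Table 4 columns use h·√(1300/n); the S-table columns use h·√(1000/n).

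| Share (n) | Measles, Table 4 | Measles, Table S1 | Hepatitis B, Table 4 | Hepatitis B, Table S2 |
|---|---|---|---|---|
| 10% (390) | ±3.1% | ±2.6–3.1% | ±2.7% | ±2.1–2.3% |
| 15% (585) | ±2.5% | ±2.1–2.5% | ±2.2% | ±1.7–1.9% |
| 20% (780) | ±2.2% | ±1.8–2.2% | ±1.9% | ±1.5–1.6% |

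At n = 1,000, Table S1 itself gives 1.61% to 1.95% for measles, still under 2%.

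**4. CMV.** Table 4 gives 2.64% at 1,300, which exceeds 2% whatever happens in Brussels. By the same scaling, ±2% needs 1300·(2.64/2)² = 2,265 samples in a region. Three such regions would need 6,795, against a total of 3,900.

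**The case against.** The strongest reply is that the main text has already dealt with this. It says the equal split is unfeasible and that Brussels intervals will be wider. Appendix 5 is worded as a recommendation, which the main text then modifies, and Table 4's caption states its own condition. The precision aim in the Sample size section covers overall and age-group estimates, with no ±2% target by region. All of this is correct: nothing is concealed, and accepting less precision in Brussels is a legitimate choice. What the reply leaves is that the main text gives a direction without a number, while Appendix 5 keeps the numbers and the ±2% conclusion under the label of the final allocation.

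Three stronger readings are tempting, and the documents do not support them.

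- A reader might infer that ±2% is lost in Brussels for measles and hepatitis B. That depends on a count the documents do not give. At a 20% share, scaling Table S1 gives ±1.8% to ±2.2% for measles, so it could go either way.
- A reader might infer that the adopted allocation makes a Brussels gap of 2 to 3 points undetectable. Compare Brussels with the rest of the 3,900, using Table 4 scaling for measles. The half-width of the difference is √(1.69²+1.20²) = 2.07 points at the equal split, so 2 points is unresolved even there. It is √(2.18²+1.09²) = 2.4 at a 20% share and √(2.52²+1.06²) = 2.7 at 15%, so an observed 3-point gap still excludes zero. Only at 10%, with √(3.09²+1.03²) = 3.3, does it not.
- A reader might infer a broken promise for Brussels adolescents. Table 5 is national, and no region-by-age precision is claimed anywhere.

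**Conclusion.** The point holds as an unreconciled precision statement. Table 4's regional row does not describe Brussels under the adopted plan: with fewer than 1,300 samples, 1.69% and 1.45% will not be reached. If the total stays at 3,900, at least one other region receives more than 1,300 and is estimated more precisely than stated, so a single regional row no longer fits.

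Loss of ±2% in Brussels is possible but not shown. For measles the limit lies between about 650 and 950 samples, and for hepatitis B between about 420 and 685, depending on which of the protocol's tables is scaled. At assumed shares of 10% to 20%, Table 4 scaling gives ±3.1% to ±2.2% for measles and ±2.7% to ±1.9% for hepatitis B. These figures assume 1/√n scaling and the same age mix in each region, with no allowance for clustering by laboratory or for test error.

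The CMV part needs no assumption: the below-±2% regional conclusion contradicts Table 4 (2.64%) in every region at the full 1,300. The text beside Table 4 treats that value as tolerable, although the opening of the same section sets acceptable precision at below ±2%.

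**What to change.** - Remove the sentence in Appendix 5 that divides 3,900 equally by region, or qualify it with a reference to the Sample size section.
- Replace the single regional row of Table 4 with one row per region at the allocated counts. Until the participating laboratories are known, show Brussels over a range of n.
- Limit the below-±2% regional conclusion to the region and pathogen pairs that meet it, and take CMV out of it.
- State the expected Brussels half-width in the Sample size section, next to the sentence that accepts wider intervals.

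The limits derived above should not become fixed cut-offs in the protocol, because they move with the table used. Nor is a ±2% trigger needed for calling Brussels age-group estimates descriptive: the protocol already accepts national age-group precision of up to 3% for measles.

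The cost is a rerun of the existing simulation at the regional counts and edits to one table and a few sentences. No extra samples are needed. The drawback is a less favourable stated precision for Brussels.

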- [16] J. Schenk, S. Abrams, H. Theeten, P. Van Damme, P. Beutels, et N. Hens, « Immunogenicity and persistence of trivalent measles, mumps, and rubella vaccines: a systematic review and meta-analysis », *Lancet Infect. Dis.*, vol. 21, nº 2, p. 286-295, févr. 2021, doi: 10.1016/S1473-3099(20)30442-4.

5. Supplementary Materials of Appendix 5

[figure not shown]

Figure S1. Vaccination coverages (MMR1 in blue and MMR2 in orange) for (a) Flanders, (b) Wallonia, (c) Brussels.

[figure not shown]

Figure S2. Age structure of samples under the population-based allocation, based on 2021 demographic data.

[figure not shown]

Figure S3. Age distribution of samples under the survey-based allocation, based on the empirical age structure observed in the 2013 serological survey (measles).

sample size	structure	precision	overall prevalence
1000	sero	0,0195	0,903
1000	рор	0,0161	0,903
1000	unif	0,0184	0,903
2000	sero	0,0152	0,902
2000	рор	0,0123	0,903
2000	unif	0,0129	0,902
3000	sero	0,0120	0,903
3000	рор	0,0102	0,902
3000	unif	0,0110	0,903
4500	sero	0,0097	0,903
4500	рор	0,0089	0,902
4500	unif	0,0085	0,902

Table S1. Precision of the overall prevalence for measles.

[figure not shown]

Figure S4. Observed seroprevalence and smoothed estimates in 1993 for HBV. Age-specific seroprevalence (red dots with binomial confidence intervals) and fitted GAM estimates (black line) based on 1993 serological data. The generalised additive model was fitted using a complementary log-log link with a smooth term for age.

sample size	structure	precision	overall prevalence
1000	sero	0,01334	0,05541
1000	pop	0,01291	0,05489
1000	unif	0,01453	0,05473
3000	sero	0,00785	0,05511
3000	рор	0,00748	0,05491
3000	unif	0,00824	0,05443
6000	sero	0,00552	0,05482
6000	pop	0,00539	0,05488
6000	unif	0,00582	0,05473
9000	sero	0,00468	0,05471
9000	рор	0,00489	0,05498
9000	unif	0,00489	0,05501

Table S2. Precision of the overall prevalence for Hepatitis B.

[figure not shown]

Figure S5. Observed seroprevalence and smoothed estimates in 2011 for CMV.

Age-specific seroprevalence (red dots with binomial confidence intervals) and fitted GAM estimates (black line) based on 2011 serological data. The generalised additive model was fitted using a complementary log-log link with a smooth term for age.

sample size	structure	precision	overall prevalence
1000	sero	0,03476	0,349
1000	рор	0,03053	0,349
1000	unif	0,02886	0,348
3000	sero	0,02002	0,348
3000	рор	0,01585	0,348
3000	unif	0,01540	0,348
